## 7 Reporting and Documentation of Results

### 7.1 Evaluation of Efficacy (or Activity)

Response and progression will be evaluated in this study using the international criteria proposed by the Response Evaluation Criteria in Solid Tumors (RECIST) 1.1 criteria. Changes in only the longest diameter (unidimensional measurement- LD) of the tumor lesions are used in the RECIST criteria.

**Note:** lesions are either measurable or non-measurable using the criteria provided below. The term "evaluable" in reference to measurability will not be used because it does not provide additional meaning or accuracy.

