### 7.3 Disease Parameters

#### **Measurable disease**

Measurable disease is defined as lesions (or tumors) that can be accurately measured in at least one dimension (longest diameter to be recorded) with a minimum size of 10mm by CT scan (irrespective of scanner type) or bone scan. All tumor measurements will be recorded in millimeters or decimal fractions of centimeters. Previously irradiated lesions are considered non-measurable except in cases of documented progression of the lesion since the completion of radiation therapy.

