#### **Target lesions**

All measurable lesions up to a maximum of 5 lesions total (and a maximum of two lesions per organ) representative of all involved organs should be identified as target lesions and recorded and measured at baseline. Target lesions will be selected on the basis of their size (lesions with the longest diameter) and their suitability for accurate repeated measurements (either by imaging techniques or clinically). A sum of the longest diameter (LD) for all target lesions will be calculated and reported as the baseline sum LD. The baseline sum LD will be used as reference by which to characterize the objective tumor response.

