#### **7.3.1.3 Response Criteria**

##### **Evaluation of Target Lesions**

###### **Complete Response (CR)**

Disappearance of all target lesions, determined by two separate observations conducted not less than 4 weeks apart. Any pathological lymph nodes (whether target or non-target)

must have reduction in short axis to <10 mm (the sum may not be “0” if there are target nodes). There can be no appearance of new lesions.

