**Progressive Disease (PD)**

At least a 20% increase in the sum of the SLD of target lesions, taking as reference the smallest sum SLD recorded since the treatment started and minimum 5 mm increase over the nadir, or the appearance of one or more new lesions.

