**Evaluation of Non-Target Lesions**

**Complete Response (CR)**

Disappearance of all non-target lesions and normalization of tumor marker level. All lymph nodes must be non-pathological in size (< 10 mm short axis).

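### Target lesions and soft-tissue progression are defined by longest diameter alone, while complete response judges lymph nodes by short axis, so nodal change can be misclassified in the primary endpoint

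*Combined protocol and SAP*

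**What the plan says.** Section 7.1 names the standard: "Response and progression will be evaluated in this study using the international criteria proposed by the Response Evaluation Criteria in Solid Tumors (RECIST) 1.1 criteria". It continues: "Changes in only the longest diameter (unidimensional measurement- LD) of the tumor lesions are used in the RECIST criteria". The Efficacy Assessments row of the abstract says the same. A note in 7.1 then points to the protocol's own text for measurability: "lesions are either measurable or non-measurable using the criteria provided below".

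That text is in Section 7.3. Measurable disease is defined with "longest diameter to be recorded) with a minimum size of 10mm by CT scan". Target lesions are drawn from all measurable lesions, up to five in total and two per organ, and "A sum of the longest diameter (LD) for all target lesions will be calculated and reported as the baseline sum LD". Neither paragraph has a separate rule for lymph nodes.

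In Section 7.3.1.3, progression of target lesions is "At least a 20% increase in the sum of the SLD of target lesions" over the smallest recorded sum, with a rise of at least 5 mm. Partial response and stable disease also refer to the sum of longest diameters. Complete response uses the other axis. Pathological nodes, target or non-target, "must have reduction in short axis to <10 mm", and the text adds that the sum need not reach zero when there are target nodes. For non-target lesions, "All lymph nodes must be non-pathological in size (< 10 mm short axis").

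RECIST progression is an event in the primary endpoint in both Section 2.4.1 and Section 8.4.2.

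**The concern.** Lesion selection, the target sum and progression run on one axis, while complete response in nodes runs on the other. The remark that the sum need not be zero fits a sum into which nodes enter by short axis, yet the sum is defined by longest diameter. Nothing sets a short-axis minimum for choosing a node at baseline.

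Two errors follow. A node that the protocol itself would call non-pathological can be a target, and its elongation can count as progression. A node that thickens across its short axis can be read as stable. Both change whether a patient counts as progression-free at 16 weeks, which is what the futility rule (10 or fewer of 18) and the final rule (36 or more of 54) count. Section 3.1 expects at least 3 to 5 centres. A site that follows Sections 7.1 and 7.3 literally and a site that imports nodal rules from the named RECIST version could classify the same scans differently.

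**Working it through.** **1. The plan's own design figures.** Inputs from Section 8.2.1: 18 then 54 patients, stop at 10 or fewer, reject at 36 or more, null 55%, alternative 75%.

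- Early stopping = P(X1 ≤ 10 | 18, p).
- Rejection = Σ over x1 = 11 to 18 of P(X1 = x1) × P(X2 ≥ 36 − x1 | 36, p).

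At p = 0.55, early stopping is 0.6085 and type I error 0.0477. At p = 0.75, power is 0.9007. The stated 60.9%, 0.048 and 90.0% reproduce, so the design arithmetic is not in question.

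**2. Which axis applies where.**

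| Step | Axis in the text | Section |
|---|---|---|
| Measurable, 10 mm minimum | Longest diameter | 7.3 |
| Baseline target sum | Longest diameter | 7.3 |
| Partial response, stable disease | Longest diameter | 7.3.1.3 |
| Progression (20% and 5 mm) | Sum of the SLD (not defined; read here as longest diameters) | 7.3.1.3 |
| Complete response, nodes | Short axis < 10 mm | 7.3.1.3 |

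**3. False progression, single nodal target.** The node is 13 x 8 mm at baseline (longest diameter x short axis). It is measurable because 13 ≥ 10, and non-pathological because 8 < 10. It grows to 18 x 9 mm. The sum rises by 18 − 13 = 5 mm, and 5/13 = 38%. Both thresholds are met, while the short axis of 9 mm is still non-pathological.

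The result does not need a change of shape. With a single target, progression is reached at the larger of 1.2 × LD and LD + 5 mm:

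| Baseline (mm) | LD at progression (mm) | Short axis, same shape (mm) |
|---|---|---|
| 10 x 5 | 15 | 7.5 |
| 10 x 6 | 15 | 9.0 |
| 12 x 6 | 17 | 8.5 |
| 14 x 7 | 19 | 9.5 |

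**4. Dilution.** Add one stable 13 mm target to the 13 x 8 mm case. The sum goes from 26 to 31 mm, and 5/26 = 19.2%, below 20%. In general 5/(13 + c) ≥ 20% requires c ≤ 12 mm, so a stable companion sum above 12 mm removes the event.

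**5. Missed progression, single nodal target.** A node goes from 24 x 16 to 26 x 21 mm. By longest diameter the rise is 2 mm, 2/24 = 8%, which is stable. By short axis it is 5 mm, 5/16 = 31%, and both thresholds are met. The same dilution applies if other targets are in the sum.

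**6. Sensitivity of the decision rule (assumed rates).** The documents give no rate for either error. Let m be the fraction misclassified by week 16. False events among truly progression-free patients change p to 0.75(1 − m). Missed events among true progressors under the null change p to 0.55 + 0.45m.

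| m | Power with false events | Stage 1 stopping at a true 75% | Type I error with missed events |
|---|---|---|---|
| 0 | 0.901 | 0.057 | 0.048 |
| 2% | 0.855 | 0.077 | 0.062 |
| 5% | 0.764 | 0.115 | 0.090 |
| 10% | 0.562 | 0.201 | 0.154 |

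False events alone lower the type I error, for example to 0.034 at m = 2%.

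**The case against.** The best defence is that RECIST 1.1 is named as the standard, so its nodal rules apply and the sentence on longest diameter is only a loose description. This does not settle it. Section 7.1 says that longest diameter alone is used and refers measurability to the protocol's own criteria, which contain no nodal rule. Section 8.4.2 speaks of modified RECIST without stating the modification.

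A second defence is that no sentence tells sites to measure nodes by longest diameter or to select normal nodes. The text speaks of tumour lesions, and targets are also chosen for suitability for repeated measurement. That is correct: the problem is inferred from an absent exception. A careful reader could decline a 13 x 8 mm node, but nothing written excludes it.

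Three limits stand in full. First, the two sets of rules are not strictly incompatible. A site could sum longest diameters for partial response and progression and add the short-axis condition for complete response. A reader might infer that the criteria cannot be applied at all, but the text does not support that. Second, the false-progression example needs a sole or dominant nodal target, as the dilution step shows. Third, the misclassification rates are assumptions. A reader might take the 10% row as a forecast that power falls to 56%, but nothing in the documents supports such a rate. Bone metastasis is required for entry (Section 3.3.1), patients without measurable disease are eligible (Section 7.3), and the share with any nodal target is not given.

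**Conclusion.** The inconsistency is real and can be shown from the protocol alone. It feeds a component of the primary endpoint and should be corrected. Its demonstrated reach is limited to patients whose target sum consists wholly or mainly of lymph nodes. In them, as written, non-pathological nodes can produce a progression event and short-axis growth can be missed.

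The size of the effect on the 10/18 and 36/54 counts is unknown. The two errors pull in opposite directions: false events cost power and favour futility stopping, while missed events inflate the type I error. At an assumed 2%, power would be about 86% instead of 90%, or the type I error about 0.062 instead of 0.048. These figures show that the rule is sensitive to a few reclassified patients, not what will happen. The stated sample size and error rates are correct for the rates assumed in Section 8.2.1.

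**What to change.** Amend the wording as follows.

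- **Section 7.1 and the Efficacy Assessments row of the abstract:** delete the statement that only the longest diameter is used.
- **Section 7.3:** state that nodes are measured by short axis at baseline and enter the target sum by short axis. State that a node under 10 mm short axis is non-pathological and cannot be a target lesion, in line with the complete-response rules in 7.3.1.3. State the minimum nodal short axis for target selection, taken from the RECIST 1.1 version already named; the protocol gives no figure for this, so it must be checked against that source.
- **Target lesions (7.3), and Partial Response, Progressive Disease and Stable Disease (7.3.1.3):** replace the sum of longest diameters, including the wording *sum of the SLD*, by a sum of diameters: longest for non-nodal lesions, short axis for nodal lesions.
- **Section 8.4.2:** refer to the same criteria, or say what the modification of RECIST is.

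The cost is protocol text and a line on the tumour measurement form. Scans and readers are unchanged. Somewhat fewer patients will have measurable disease, but Section 7.3 keeps patients with non-measurable disease eligible.

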### 7.2 Definitions

#### **Evaluable for toxicity**

All patients will be evaluable for toxicity from the time of their first treatment with the study drug.

#### **Evaluable for objective response**

Only those patients who have measurable disease present at baseline, have received at least one cycle of therapy, and have had their disease re-evaluated will be considered

evaluable for response. These patients will have their response classified according to the definitions stated below. (Note: Patients who exhibit objective disease progression prior to the end of Cycle 1 will also be considered evaluable.)

### 7.3 Disease Parameters

#### **Measurable disease**

Measurable disease is defined as lesions (or tumors) that can be accurately measured in at least one dimension (longest diameter to be recorded) with a minimum size of 10mm by CT scan (irrespective of scanner type) or bone scan. All tumor measurements will be recorded in millimeters or decimal fractions of centimeters. Previously irradiated lesions are considered non-measurable except in cases of documented progression of the lesion since the completion of radiation therapy.

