### **2.4 Endpoints**

#### **2.4.1 Primary Endpoints**

Radiographic progression free survival (rPFS). This is defined from study start until one of the following events occurs:

- $\geq 2$  new bone lesions on Technetium bone scan. If  $\geq 2$  new lesions are detected at or 12 weeks following initiation of treatment, progression must be confirmed by the presence of  $\geq 2$  or more additional lesions to rule out bone scan flare as a cause of the radiographic changes.

- RECIST-defined tumor progression.
- Clinical deterioration requiring a change in prostate cancer therapy, or at clinician discretion
- Surgery or Radiation to treat a prostate cancer related indication
- Death from any cause.

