- c. Other second-generation investigational anti-androgen/androgen-receptor targeted therapies, including ARN-509. Primary resistance will be defined as:
- i. No PSA decline
  - ii. PSA decline less than 50% after 12 weeks of enzalutamide therapy
  - iii. PSA progression within 12 weeks of enzalutamide treatment (by PCWG2 criteria), after initial response to therapy
  - iv. Objective progression, by RECIST criteria for soft tissue lesions and by modified PCWG2 criteria for bone lesions within 12 weeks of starting enzalutamide treatment
  - v. Unequivocal clinical progression (per the treating provider's discretion) within 12 weeks of starting enzalutamide treatment
- d. Combination therapy with abiraterone, enzalutamide and/or other second-generation investigational anti-androgen/androgen-receptor targeted therapies, including ARN-509. Primary resistance to combination therapy will be defined as:
- No PSA decline
  - PSA decline less than 50% after 12 weeks of abiraterone and enzalutamide therapy
  - PSA progression within 12 weeks of abiraterone and enzalutamide treatment (by PCWG2 criteria), after initial response to therapy
  - Objective progression, by RECIST criteria for soft tissue lesions and by modified PCWG2 criteria for bone lesions within 12 weeks of starting abiraterone and enzalutamide treatment
  - Unequivocal clinical progression (per the treating provider's discretion) within 12 weeks of starting abiraterone and enzalutamide treatment
- e. Sequenced therapy, including any of the following:
- i. Abiraterone acetate followed by enzalutamide
    - 1. Primary resistance will be defined per criteria for abiraterone monotherapy primary resistance, section 3.3.1, item 5a
  - ii. Enzalutamide followed by abiraterone acetate
    - 1. Primary resistance will be defined per criteria for enzalutamide monotherapy primary resistance, section 3.3.1, item 5b
  - iii. Other second-generation investigational anti-androgen/androgen-receptor targeted therapies, including ARN-509.

1. Primary resistance will be defined per criteria for other investigational anti-androgen monotherapy primary resistance, section 3.3.1, item 5c
7. Presence of 1 or more bone metastasis.
8. ECOG Performance status 0 or 1.
9. Prior and ongoing zoledronic acid or denosumab therapy is allowed.
10. Prior therapy with radium-223 is allowed.

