#### **7.3.1.2 Methods for Evaluation of Non-Measurable Disease**

PSA levels will be monitored monthly.

Bone scans obtained after the baseline evaluation will be used to evaluate post-treatment changes. Outcome is listed as new lesions or no new lesions. Progression is defined as the appearance of 2 or more new lesions. This is based on the PCWG2 criteria in standard practice for trials in metastatic CRPC.

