## 8.4 Analyses Plans

### 8.4.1 Analysis Population

All patients who receive at least 1 dose of selinexor will be evaluated for response.

Only those patients who have measurable disease present at baseline, have received at least one cycle of therapy, and have had their disease re-evaluated will be considered evaluable for response. All analyses will be performed with respect to all patients treated

with selinexor, regardless of prior therapy, with a separate analysis performed according to prior treatment status with cohorts of patients as follows:

- (A) Prior abiraterone only
- (B) Prior enzalutamide only
- (C) Prior concomitant therapy with abiraterone and enzalutamide
- (D) Prior sequenced therapy with abiraterone and enzalutamide

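### Counting bone-scan lesions of 10 mm or more as measurable contradicts the protocol's own bone-scan rules and could, on a literal reading, create unconfirmed progression events in the primary endpoint

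*Combined protocol and SAP*

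**What the plan says.** **Measurability and target lesions.** Section 7.3 (Measurable disease) requires lesions that can be measured accurately in at least one dimension, "with a minimum size of 10mm by CT scan (irrespective of scanner type) or bone scan". The Target lesions paragraph makes measurable lesions target lesions, up to five in total and two per organ, chosen by size and by suitability for accurate repeat measurement. It does not exclude bone.

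**Progression.** Section 7.3.1.3 calls progression on target lesions when their sum rises by at least 20% and at least 5 mm over the smallest recorded sum, "or the appearance of one or more new lesions". The non-target rule likewise counts one new lesion. Neither excludes bone-scan lesions or mentions flare.

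**Primary endpoint.** Section 2.4.1 lists "RECIST-defined tumor progression" as an event in its own right. The confirmation meant "to rule out bone scan flare as a cause of the radiographic changes" belongs only to the separate item on two or more new bone lesions. The event list in Section 8.4.2 also has a RECIST item with no restriction by site.

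**Text pointing the other way.** Section 7.3 (Non-measurable disease) says that patients without measurable disease are assessed by PSA and serial bone scans. The paragraph on non-measurable bone disease allows two bone-scan readings, new lesions or none, and requires confirmation of new lesions at the first reassessment. Section 7.3.1.2 repeats this: "Outcome is listed as new lesions or no new lesions". The rPFS paragraph of Section 8.4.2 confines RECIST progression to soft tissue. The Non-target lesions paragraph says that bone lesions may be measurable at 1 cm or more on MRI, a modality that the measurable-disease definition does not name.

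**The concern.** The protocol has two systems for judging progression: RECIST diameters for measurable lesions, and a new-lesion count with a flare safeguard for bone scans. The measurable-disease definition lets bone-scan lesions into the first system while other sections keep them in the second. Nothing says which text governs, and in a multicentre study two sites could score the same patient differently.

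Radiographic progression-free status at 16 weeks decides both stage-1 stopping and the final result. If an apparent enlargement on bone scan, or a single new focus, is scored under RECIST, the patient becomes a progression without the confirmation that the protocol requires of bone-scan findings. Inclusion criterion 7 of Section 3.3.1 requires "Presence of 1 or more bone metastasis", so the ambiguity is not confined to an unusual subgroup, although not every such lesion would qualify as measurable.

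**Working it through.** **Step 1. Can a bone-scan lesion reach the primary endpoint through RECIST on the literal text?**

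| Link | Section | Open or closed |
|---|---|---|
| Lesion of at least 10 mm on bone scan is measurable | 7.3, Measurable disease | Open |
| Measurable lesions become target lesions; bone not excluded | 7.3, Target lesions | Open, if accurately and repeatably measurable |
| Target sum up by at least 20% and 5 mm is progression; no flare step | 7.3.1.3 | Open |
| One new lesion is progression; bone scan not excluded | 7.3.1.3, target and non-target rules | Open |
| RECIST progression is a separate event, no site limit | 2.4.1 and the 8.4.2 event list | Open |
| RECIST progression limited to soft tissue | 8.4.2, rPFS paragraph | Closed |
| Bone scans read only as new or no new lesions | 7.3, non-measurable bone disease; 7.3.1.2 | Closed for diameters |

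The route is permitted by one set of passages and shut by another.

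**Step 2. What growth would be needed?** The rule applies to the sum of target diameters. The 5 mm condition binds when 20% of the sum is below 5 mm, that is, for sums under 5 / 0.20 = 25 mm. A lone 10 mm target must reach 15 mm. With a target sum of 50 mm, the required rise is 0.20 × 50 = 10 mm.

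**Step 3. Reproduce the design (Section 8.2.1).** Inputs: 18 patients in stage 1, stop at 10 or fewer progression-free; 54 in total, reject at 36 or more; null 55%, alternative 75%. With X1 ~ Bin(18, p) and X2 ~ Bin(36, p):

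- P(early stop) = P(X1 ≤ 10)
- P(reject) = Σ over x = 11 to 18 of P(X1 = x) · P(X2 ≥ 36 − x)

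At p = 0.55, early stopping is 0.6085 and rejection 0.0477. At p = 0.75, rejection is 0.9007. These match the stated 60.9%, 0.048 and 90.0%, so the design arithmetic is not in dispute.

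**Step 4. Illustrate the effect of false progressions.** Let d be the percentage points of patients wrongly called progressed by week 16. The documents give no value for d; those below are assumptions. The observed rate is p − d.

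| d (points) | Rate if true 75% | Power | Stage-1 stop at true 75% | Rate if true 55% | Type I error |
|---|---|---|---|---|---|
| 0 | 75% | 0.901 | 0.057 | 55% | 0.0477 |
| 3 | 72% | 0.797 | 0.101 | 52% | 0.0179 |
| 5 | 70% | 0.702 | 0.141 | 50% | 0.0085 |
| 10 | 65% | 0.415 | 0.272 | 45% | 0.0009 |

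If misclassification is instead a fraction q of the truly progression-free patients, the rate is 0.75 × (1 − q). Taking q = 5% gives 71.25% and power 0.764; q = 10% gives 67.5% and power 0.562. On either definition the error is one-directional: power and type I error both fall.

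**The case against.** The strongest reply is that the intent is clear and practice would follow it. The rPFS paragraph of Section 8.4.2 restricts RECIST to soft tissue, and inclusion criteria 5 and 6 make the same split. Section 7.3 has bone scans recorded on the tumor measurement forms as new or no new lesions, with no place for a diameter. The requirements for accurate and repeatable measurement, and the general exclusion of previously irradiated lesions, would keep many bone-scan lesions from becoming targets. All of this stands, and it is why the true effect may be close to zero. It does not settle which text governs, because the event lists in Sections 2.4.1 and 8.4.2 lack the soft-tissue limit. It also does not touch the one-new-lesion rules.

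Three stronger readings might be inferred, and the documents do not support them:

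- **That 20% growth in one bone lesion is itself progression.** The rule needs a 20% rise in the sum of all targets and at least 5 mm.
- **That nearly every patient becomes measurable and the response denominator changes materially.** Criterion 7 requires a bone metastasis, not one of at least 10 mm that can be measured accurately on bone scan. Section 8.4.1 does say "Only those patients who have measurable disease present at baseline" count as evaluable for response (with further conditions), but no response rate is listed as an endpoint and Sections 8.4.2 and 8.4.3 plan no analysis of one.
- **That the trial has lost a known amount of power.** The power figures depend on assumed misclassification rates.

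**Conclusion.** The point holds as an internal inconsistency that reaches the primary endpoint. The measurable-disease definition conflicts with the sections on non-measurable disease and with the soft-tissue limit in the rPFS paragraph of Section 8.4.2. On the literal text, it could allow progression events that avoid the two-new-lesion and flare rules. The one-new-lesion rules in Section 7.3.1.3 open the same gap more directly.

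The size is unknown. If 3, 5 or 10 percentage points of patients were affected, power at a true 75% would be about 80%, 70% or 41% instead of 90%; if none were, nothing would change. The risk is a false negative, including wrongful stopping at stage 1, not a false claim of activity. No change to sample size or decision boundaries follows. The text should be corrected because the contradiction bears on the endpoint that decides the trial and costs little to remove.

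**What to change.** 1. In Section 7.3 (Measurable disease), delete the last three words of the phrase "with a minimum size of 10mm by CT scan (irrespective of scanner type) or bone scan".
2. In Section 2.4.1 and the event list of Section 8.4.2, limit RECIST progression to soft tissue, as the rPFS paragraph of Section 8.4.2 already does.
3. In Section 7.3.1.3, exclude bone-scan lesions from the one-new-lesion rule for both target and non-target progression, and state that they are judged only under the bone-scan rules in Section 7.3 (non-measurable bone disease) and Section 7.3.1.2.
4. Reconcile the sentence in the Non-target lesions paragraph on bone lesions measurable by MRI with the definition of measurable disease, which does not name MRI.

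The first change alone is not enough, because the one-new-lesion rules would still let a single bone-scan lesion count. The cost is a short wording amendment, with no added patients, visits or scans. If patients have already been assessed, progressions recorded under RECIST on bone-scan findings alone should be identified and re-read under the corrected definitions.
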